2.2.4.4 Subgroup Analyses

Subgroup analyses will be conducted on the primary and secondary endpoints stratifying by severity of atopic dermatitis (moderate or severe), defined as an IGA score of 3=moderate or 4=severe at the Baseline/visit 2 visit, which is consistent with the AD severity used for the entrance criteria in the study. Statistical testing for this subgroup analyses will be limited to the primary efficacy endpoint but summary statistics will be provided for all secondary efficacy endpoints.

2.2.5 Study Assessment Time Points

The study consists of seven protocol-specified visits which will be assessed as nominal visits from an analysis perspective:

- Visit 1/Screening visit (Day -30 to -1): Once informed consent has been obtained, the Investigator will assign a Patient Number and the subject will undergo the screening procedures. Following completion of a successful screening visit, patients will begin the comparative treatment period (8 weeks).
- Visit 2/Baseline (Day 0): At the start of the comparative treatment period, after confirmation of continued eligibility, patients will be randomly assigned to one of the three treatment regimens. Study medication is dispensed at Visit 2. The first dose of study medication will be carried out at the site once all baseline assessments have been completed. The patient will carry out their second dose of study medication in the evening of Day 0.
- Visits 3, 4 and 5: Follow-up visits at Week 2 (Day 14 ± 2 days), Week 4 (Day 28 ± 2 days) and Week 6 (Day 42 ± 2 days) respectively.
- Visit 6 – End of Treatment (EOT): Week 8 (Day 56 ± 2 days) for subjects who complete 8 weeks of treatment; earlier for subjects who discontinue treatment prematurely.
- Visit 7/Week 10: End of Study visit (Day 70 ± 3 days) for all subjects.
- Unscheduled Visits: Unscheduled visits may occur when a patient needs to make a visit in between the scheduled visit dates due to an AE, difficulty complying with the study protocol requirements, or a significant change in their disease state. All procedures that are medically necessary should be followed.

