7.5 Withdrawal of Patients

Patients have the right to withdraw from the study at any time for any reason without penalty. The investigator must explain this to the patient and that this will in no way prejudice their future treatment. The investigator also has the right to withdraw patients from the study if he feels it is in the best interest of the patient or if the patient is uncooperative or non-compliant. It is understood by all concerned that an excessive rate of withdrawal can render the study uninterpretable, therefore, unnecessary withdrawal of patients should be avoided. Should a patient decide to withdraw, all efforts will be made to complete and report the observations, particularly the follow-up examination, as thoroughly as possible.

The investigator or one of his or her staff members should contact the patient either by telephone or through a personal visit to determine as completely as possible the reason for the withdrawal, and record the reason in patient's source document and CRF. A complete final early termination evaluation at the time of the patient's withdrawal should be made with an explanation of why the patient is withdrawing from the study. If the reason for removal of a patient is an adverse event or an abnormal laboratory test result, the principal specific event or test will be recorded. Patients who discontinue the study before Week 8/Visit 6 visit will be asked to come for an early termination visit as soon as possible and have the assessments listed at Week 8/Visit 6 performed. They will also be asked to return two weeks later for the safety assessments listed at Week 10/Visit 7.

There will be two main categories for withdrawals from the study: “complete withdrawal” and “withdrawals from investigational product”.

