7.5.1 Complete Withdrawal

Discontinuation of investigational product and all efficacy and safety evaluations. Standard reasons for withdrawing from further participation in the study and from the follow-up visits may be:

- Patients decision (withdrawal of consent to participate)
- Patient lost to follow-up (drop-out)

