8 STUDY CONDUCT

8.1 Study Schedule

During the study, six visits to the clinic are scheduled at least one week after the screening visit: one at the start of the comparative treatment period/baseline (Day 0/Visit 2) and five in the comparative treatment period (Week 2/Visit 3, Week 4/Visit 4, Week 6/Visit 5 and Week 8/Visit 6). A final safety follow-up visit (Visit 7) will be conducted two weeks after Visit 6 or two weeks after the final visit attended if the patient does not complete the study. The baseline visit must be performed, at the latest 30 days after the screening visit.

Patients who discontinue the study early will be asked to attend the investigative site as soon as possible so that assessments scheduled for Visit 6 can be conducted at an Early Termination visit.

In the event that treatment is occurring, a wash out period of up to 4 weeks may be necessary. At the Screening visit, after giving informed consent to participate, patients will be assessed using the screening examinations. Eligible patients with confirmed AD using the Hanifin and Rajka criteria and who meet all the inclusion criteria and do not meet the exclusion criteria at the baseline visit will be enrolled.

During the treatment period and follow-up period patients will be restricted from using any other treatment for AD, with the exception of the same emollients they have been consistently using at the baseline visit. Any medication (prescription as well as OTC drugs) or therapeutic intervention deemed necessary for the patient, and which in the opinion of the Investigator do not interfere with the safety and efficacy evaluations, may be continued. A list of ‘medications and therapeutic regimens excluded from the study’ is defined below (Section 9.2.11.2).

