8.2.8 Week 10 (Visit 7) / Follow up

Two weeks after Visit 6 (or early withdrawal visit), patients will return to the investigational site and the final procedures/assessments will occur:

- Samples for clinical laboratory safety tests (haematology, serum biochemistry, urinalysis as detailed in Section 9.2.4) - Only if clinically significant change from baseline in safety lab results at Week 8 / Visit 6
- Pharmacokinetic Sampling (as detailed in Section 9.2.7)
- Vital signs (blood pressures, heart rate and body temperature), as detailed in Section 9.2.3);

- Physical examination (as detailed in Section 9.2.2)
- Body Surface Area (as detailed in Section 9.1.4)
- Investigator's Global Assessment (as detailed in Section 9.1.1)
- Eczema Area and Severity Index (EASI) (as detailed in Section 9.1.2)
- NRS Pruritus assessment (as detailed in Section 9.1.3)
- Dermatology Life Quality Index (DLQI) Questionnaire (as detailed in Section 9.1.5)
- Patient Orientated Eczema Measure (as detailed in Section 9.1.6)
- Patient Global Impression of Severity Questionnaire as detailed in Section 9.1.7)
- Patient Global Impression of Change Questionnaire as detailed in Section 9.1.8)
- Concomitant medication assessment (as detailed in Section 9.2.11)
- AE assessment (as detailed in Section 11)

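### For early leavers, Visit 7 comes two weeks after the early termination visit but carries the Week 10 label; no SAP rule keeps such values out of the Week 10 secondary analyses

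*SAP*

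**What the plan says.** **Timing.** SAP 2.2.5 sets "Visit 7/Week 10: End of Study visit (Day 70 ± 3 days) for all subjects". The same section says of the seven visits: "which will be assessed as nominal visits from an analysis perspective". Visit 6 may take place "earlier for subjects who discontinue treatment prematurely". Protocol 8.1 puts the final follow-up visit "two weeks after Visit 6 or two weeks after the final visit attended if the patient does not complete the study". Protocol 8.2.8 agrees: "Two weeks after Visit 6 (or early withdrawal visit), patients will return to the investigational site".

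**Who comes back.** Under Protocol 7.5, patients who leave before Week 8 "will be asked to come for an early termination visit as soon as possible". It continues: "They will also be asked to return two weeks later for the safety assessments listed at Week 10/Visit 7". SAP 2.1 repeats this, but also places the end-of-study visit ten weeks after treatment for everyone. Complete withdrawal (Protocol 7.5.1) means "Discontinuation of investigational product and all efficacy and safety evaluations". Patients who stop only the study drug (Protocol 7.5.2) stay in follow-up, with efficacy assessed.

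**What is measured.** Protocol 8.2.8 lists IGA, EASI, pruritus NRS, DLQI, POEM, PGI-S and PGI-C at Visit 7, and its opening sentence covers early withdrawals. The closing text of Protocol 8.2.7, the combined Week 8 and ET section, also announces efficacy assessments at Visit 7. Protocol 7.5 and SAP 2.1 name safety assessments only.

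**What is analysed.** SAP 2.2.12.2 plans separate Week 10 models for IGA response, the 2-point IGA decrease, EASI and NRS. NRS is the average of the diary values since the previous visit. The full analysis set (FAS) is everyone randomised and dosed. The SAP gives no date rule for a Visit 7 that follows an ET visit.

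**The concern.** The concern is limited to patients who leave the study early, attend an ET visit and return for follow-up. Their Visit 7 is tied to the ET date, yet it carries a label defined by Day 70. Because visits are analysed by label, a value taken weeks before Day 67 would be modelled alongside completers' Day 70 values.

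The Week 10 secondary endpoints are defined as results at Week 10. A record near Day 28, after at most about two weeks of drug, is a different quantity, all the more because Protocol 6.1 expects the effect to build to its maximum over 4 to 6 weeks. If the plan is silent, someone will have to decide after seeing the data which records count as Week 10.

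**Working it through.** **Inputs.** Visit 6 on Day 56 ± 2 and Visit 7 on Day 70 ± 3 (SAP 2.2.5; Protocol Appendix 1). Interval from ET visit to Visit 7: 14 days (Protocol 8.1 and 8.2.8). The documents attach the 3-day window to Day 70; applying it to ET + 14 is my assumption, and it favours the plan.

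**The plan's own figure.** For a completer, 56 + 14 = 70, and 70 ± 3 gives Days 67 to 73. This reproduces the SAP.

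**Early leavers.** Visit 7 day = ET day + 14, at the latest ET day + 17.

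| ET visit day | Visit 7, nominal | With ± 3 days | Days before Day 67: nominal | Days before Day 67: latest |
|---|---|---|---|---|
| 14 | 28 | 25 to 31 | 39 | 36 |
| 28 | 42 | 39 to 45 | 25 | 22 |
| 42 | 56 | 53 to 59 | 11 | 8 |
| 49 | 63 | 60 to 66 | 4 | 1 |
| 50 | 64 | 61 to 67 | 3 | 0 |
| 53 | 67 | 64 to 70 | 0 | in window |

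**Thresholds.** The latest possible Visit 7 is too early when ET + 17 < 67, that is, ET on Day 49 or before. The nominal Visit 7 is too early when ET + 14 < 67, that is, ET on Day 52 or before. Before Day 50 is therefore the conservative limit.

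**NRS diary.** At nominal timing, a leaver's average covers Days ET + 1 to ET + 14 and a completer's covers Days 57 to 70. They share no day when ET + 14 ≤ 56, so for ET up to Day 42. With all windows used, the earliest completer average starts on Day 55 (Visit 6 on Day 54), and ET + 17 ≤ 54 gives ET up to Day 37.

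**Who can be affected.** Complete withdrawals contribute no Visit 7. Patients who stop only the drug stay on the visit schedule and have a true Day 70 visit. That leaves study leavers who return after ET and either have efficacy scored (Protocol 8.2.8) or keep the NRS diary. The documents give no dropout rate, so this group cannot be counted.

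**Wording in SAP 2.1.** Taken literally, ten weeks after an end of treatment on Day 56 is 56 + 70 = Day 126, which contradicts Day 70. It could be a slip for two weeks after treatment or for ten weeks after baseline.

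**The case against.** The affected group may be empty. The sentences written specifically for early leavers, in Protocol 7.5 and SAP 2.1, limit the return visit to safety. If sites follow them, no IGA or EASI exists after ET and only a continued diary remains as a route. This stands as a limit on how many records are affected. It does not remove the point, because Protocol 8.2.8 covers the same visit and lists efficacy, so a site could follow either.

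The SAP could also be read as planning a true Day 70 visit for everyone plus a separate safety return for leavers. That reading is possible from SAP 2.1 but conflicts with Protocol 8.1 and 8.2.8, which give a single follow-up visit, two weeks after the last one.

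Excluding these records moves the Week 10 analysis towards completers, within a GENMOD analysis that SAP 2.2.6 describes as valid under MCAR. The only planned sensitivity analysis for missing data concerns Week 8/Exit. This objection is sound and is met by an added sensitivity analysis, not by keeping a Day 28 value as Week 10.

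Two stronger readings are tempting. A reader might infer that the Week 10 treatment difference is diluted by a calculable amount, for example by treating leavers as non-responders mixed in with completers. That calculation shows the effect of counting non-responders, which may be right in an FAS analysis. It does not measure mistiming. For that one would need to know how often status at ET + 14 differs from status at Day 70, and the documents do not say. A reader might also infer that the Week 8 to 10 sustained-efficacy and shift analyses are distorted. In the FAS this happens only if the ET record is also labelled Week 8; the per-protocol shift table contains only patients who completed the study. If the last dose is taken the day before ET (Protocol 10.3), such a pair spans about the same two weeks off drug as a completer's.

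**Conclusion.** The point holds as a minor one. Under the plan as written, an efficacy value from a Visit 7 that follows an ET visit before Day 50 would enter the Week 10 secondary models although it predates Day 67, by 39 days at nominal timing for an ET visit on Day 14 and by 11 days for one on Day 42. The day arithmetic is exact, given the 14-day interval.

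The consequence depends on how many leavers return and have efficacy recorded. That number is unknown and may be zero, and neither the direction nor the size of any bias can be computed from the documents. Secondary and exploratory Week 10 results are exposed. The Week 8 primary is not affected through Visit 7; how early ET records are labelled is a separate question.

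**What to change.** - **SAP 2.2.5 and 2.2.12:** do not use as a Week 10 value any Visit 7 record that follows an ET visit and falls before Day 67. List such records separately as post-withdrawal data. Keep completers' nominal Visit 7, even if slightly out of window.
- **Sensitivity analysis:** add a Week 10 analysis of the IGA endpoints that counts these leavers as non-responders, to cover the missing data that the exclusion creates.
- **Alignment:** make Protocol 7.5, Protocol 8.2.8 and SAP 2.1 agree on which assessments early leavers have at follow-up.
- **SAP 2.1:** correct the ten-weeks-after-treatment wording so that it gives Day 70 for completers and ET + 14 days for early leavers.

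**Cost.** SAP and protocol wording, one filter on visit dates, and one extra analysis. No new data are needed, since Protocol 6.1 has ET visits recorded, and no completer is dropped. The price is fewer Week 10 records. If 0 to 20 of 100 records per arm were removed (an assumed range with no source in the documents), standard errors would grow by a factor of about 1 to 1/√0.80 = 1.118, that is, by 0 to 12%.

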2.2.6 Methods for Handling Missing Data

PROC GENMOD will be used to account for any missing data and early withdrawal for FAS.

The GENMOD procedure will estimate the working correlation from data containing both types of missing values by using the *all available pairs* method, in which all non-missing pairs of data are used in the moment estimators of the working correlation parameters. The resulting covariances and standard errors are valid under the missing completely at random (MCAR) assumption.

A sensitivity analysis will be performed for the Week 8/Exit outcome under the missing at not random (MNAR) assumption for the primary efficacy analyses using the FAS. An extreme analysis will be used to identify the possible outcome considering two scenarios: An extreme analysis will be used to identify the possible outcome considering the worst case for both active treatments and best case for vehicle (Scenario 1) and then the reverse (Scenario 2). If any extreme cases result in statistical significance, then the maximum degree of relaxation per

treatment group still reaching statistical significance will be displayed for each scenario. A two-sided Fisher Exact Test will be utilized for these analyses.

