	
IGA-responders at other time points will also be analysed using GLMM.
 
Change from baseline endpoints (EASI, NRS, DLQI, POEM, PGI-S and PGI-C) will be analysed using mixed model with repeated measures (MMRM) with Treatment Arm as a factor and baseline value as a covariate, with the treatment-by-visit interaction term as the repeated effect to account for missing data.
 
Sensitivity analyses will be performed to assess the robustness of the Missing at Random (MAR) assumptions that underpin the GLMM methods above for imputing missing data.

SPONSOR:	DS Biopharma

LIST OF ABBREVIATIONS

15-HETrE	15-hydroxyeicosatrienoic acid
AD	Atopic Dermatitis
AE	Adverse Event
BD	Bis Die (Twice Daily)
BMI	Body Mass Index
BP	Blood Pressure
BPM	Beats Per Minute
COX	Cyclooxygenase
CRA	Clinical Research Associate
CRO	Contract Research Organisation
CRF	Case Report Form
CsA	Cyclosporin A
CTA	Clinical Trials Agreement
DGLA	Dihomo-Gamma-Linolenic Acid
DLQI	Dermatology Life Quality Index
DM	Data Manager
EASI	Eczema Area and Severity Index
EC	Ethics Committee
ECG	Electrocardiography
EDC	Electronic Data Capture
FAS	Full Set Analysis
FSH	Follicle Stimulating Hormone
GCP	Good Clinical Practice
GLP	Good Laboratory Practice
GLMM	Generalised Linear Mixed Model
ICF	Informed Consent Form
IEC	Independent Ethics Committee
ICH	International Conference on Harmonisation
IFN- γ	Interferon-Gamma
IGA	Investigators Global Assessment
IgE	Immunoglobulin E

IL	Interleukin
IMP	Investigational Medicinal Product
ISF	Investigator Site File
IWRS	Interactive Web Response System
MAR	Missing at Random
MedDRA	Medical Dictionary for Regulatory Activities
MMRM	Mixed Model with Repeated Measures
NOAEL	No Observed Adverse Event Limit
NRS	Numeric Rating Scale
OD	Once Daily
OTC	Over The Counter
PGD ₁	Prostaglandin D1
PGI-C	Patient Global Impression of Change
PGI-S	Patient Global Impression of Severity
PIS	Patient Information Sheet
PK	Pharmacokinetics
POEM	Patient Orientated Eczema Measure
PP	Per Population
PPS	Per Protocol Set
PUVA	Psoralen & Ultraviolet A
PV CRO	Pharmacovigilance Contract Research Organisation
SAE	Serious Adverse Event
SAF	Safety Analysis Set
SAP	Statistical Analysis Plan
SCORAD	Scoring of Atopic Dermatitis
SDV	Source Data Verification
SOP	Standard Operating Procedure
SPC	Summary of Products Characteristics
SUSAR	Suspected Unexpected Serious Adverse Reaction
TNF- α	Tumor Necrosis Factor-Alpha
UV-A/B	Ultraviolet-A/B
VAS	Visual Analogue Scale

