6 STUDY DESIGN

6.1 General

[figure not shown]
This is a randomised, placebo-controlled, double-blind, parallel group, multi-centre 3-arm Phase 2b study to investigate the efficacy of orally administered DS107 and the dose-response relationship between DS107 capsules and placebo in AD patients 18 years and older.

It is planned that at least 300 patients with at least 100 patients per treatment group, suffering from moderate to severe AD will be included in this study. All patients will sign an informed consent and undergo screening for study eligibility. Patients will be randomized (1:1:1) at baseline visit to either receive 2g DS107, 1g DS107 or placebo once daily for 8 weeks.

Patients will come to the clinic on 7 occasions: at Screening/Visit 1, Baseline/Visit 2, Week 2/Visit 3, Week 4/Visit 4, Week 6/Visit 5 and /Week 8/Visit 6 (end of treatment) and Week 10/Visit 7 (follow-up). Early termination visits will be recorded for patients who withdraw from the study early. All patients will exit the study at the Week 10 visit. At the screening visit, after giving informed consent to participate, patients will be assessed using the screening examinations. Patients who meet the inclusion criteria and who do not meet the exclusion criteria will be enrolled.

Unlike other oral treatments for AD (e.g. steroids) a treatment effect of DS107 capsules is not immediately expected to occur after start of treatment, but to increase constantly over time reaching its maximum effect within a time period over 4-6 weeks. Therefore, every effort should be undertaken to continue treatment with DS107 at least for 4 weeks to determine the efficacy of DS107. Patients not willing to continue to participate in the study due to the apparent lack of efficacy within the first 4 weeks of treatment therefore should be replaced. A schematic diagram of the overall timeframe of the study is given in Figure 2.

Figure 2: Study Outline

Once patients are enrolled on the study they will be restricted from using any other treatment for AD, with the exception of emollients, as defined in section 9.2.11. Any medication (prescription as well as over the counter (OTC) drugs) or therapeutic intervention deemed necessary for the patient, and which in the opinion of the Investigator do not interfere with the safety and efficacy evaluations, may be continued unless they are included in the list of ‘Concomitant Medications’ (Section 9.2.11).

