12.9.2 Primary variables

The primary variable will be the proportion of patients achieving an IGA score of 0 (clear) or 1 (almost clear) and a decrease of at least 2 points in IGA from baseline at Week 8.

The primary endpoint will be analysed using a Generalised Linear Mixed Model (GLMM) with treatment arm and baseline IGA value as factors, with the treatment-by-visit interaction term as the random effect to account for missing data. The primary analysis will be based on the FAS, and repeated for the PPS as a supportive sensitivity analysis.

The primary statistical analysis assumes “Missing At Random (MAR)” when handling missing data. The treatment effect obtained under the MAR assumption is essentially that which could have been reached if all patients had fully adhered to treatment or, in other words, the effect a patient may expect if they take the medication as directed. This is sometimes known as the ‘de jure’ or ‘efficacy’ estimand. Because of the lack of perfect adherence in practice, the ‘de facto’ or effectiveness treatment effect will also be estimated. This estimand includes assumptions regarding the treatment effects that could be expected to occur when patients discontinue treatment. The *jump to reference* method described by Carpenter et al. (J Biopharm Stat, 2013; 23(6):1352-71) will be used to estimate the de facto estimand, using the Placebo arm as the reference. This is based on the assumption that patients who discontinue from study drug have no alternative oral treatment option suitable for longer-term use and so their responses are likely to revert to those of the Placebo group. The sensitivity analyses for missing data will be performed on the FAS only.

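### The SAP replaces the protocol's MAR primary and jump-to-reference analyses of Week 8 IGA response without a stated reason, and does not settle whether an early-termination score counts as Week 8

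*SAP*

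**What the plan says.** **Protocol.** Section 12.9.2 analyses Week 8 IGA response on the FAS with a generalised linear mixed model, "with the treatment-by-visit interaction term as the random effect to account for missing data". It names the target: "The treatment effect obtained under the MAR assumption is essentially that which could have been reached if all patients had fully adhered to treatment". It adds a second, de facto target. Jump-to-reference "will be used to estimate the de facto estimand, using the Placebo arm as the reference", on the stated ground that "patients who discontinue from study drug have no alternative oral treatment option" suitable for longer-term use. The synopsis adds: "Sensitivity analyses will be performed to assess the robustness of the Missing at Random (MAR) assumptions that underpin the GLMM methods above".

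**SAP.** Section 2.2.12.1 fits PROC GENMOD with a REPEATED statement and unstructured working correlation, which is a GEE with no random effect. Section 2.2.6 uses it to deal with missing data and early withdrawal, and says: "The resulting covariances and standard errors are valid under the missing completely at random (MCAR) assumption". The sensitivity analysis in 2.2.6 is a worst-case/best-case comparison by Fisher exact test, labelled as missing not at random (MNAR). If an extreme is significant, it is relaxed to find how far significance persists. Neither MAR nor jump-to-reference appears in the SAP text available. The revision history lists only an initial version.

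**Leaving early.** Protocol 6.1 foresees patients unwilling to continue "due to the apparent lack of efficacy within the first 4 weeks of treatment therefore should be replaced". Protocol 7.5.2 lists lack of efficacy among the reasons for stopping drug while remaining in follow-up. Protocol 7.5 provides an exit assessment: "Patients who discontinue the study before Week 8/Visit 6 visit will be asked to come for an early termination visit as soon as possible", with the Week 8 assessments done then.

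**The concern.** A SAP may refine a protocol, but here it changes the missing-data assumption of the primary analysis and drops an estimand to which the protocol commits. MCAR is also hard to reconcile with a protocol that expects people to stop because the drug does not seem to work.

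The second problem is practical. Two programmers could build different primary datasets from this SAP, one treating an exit score from, say, Week 3 as the Week 8 outcome and one treating Week 8 as missing. If that choice is made after unblinding, including at the interim, it is open to suspicion.

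Third, patients who stop drug but keep attending may have an observed Week 8 score. Neither document says how that score enters the full-adherence or the jump-to-reference estimand, both of which turn on what happens when drug is stopped.

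**Working it through.** **1. Commitments side by side**

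| Item | Protocol 12.9.2 and synopsis | SAP 2.2.6 and 2.2.12.1 |
|---|---|---|
| Primary model | Mixed model (GLMM) | GEE (PROC GENMOD) |
| Assumption stated | MAR | MCAR, for covariances and standard errors |
| De facto effect | Jump-to-reference, placebo | None |
| Departure from assumption | Sensitivity analyses of MAR | Extreme-case/relaxation (MNAR) |

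**2. Is an early-termination score Week 8 data?**

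- Suggesting yes: SAP 2.2.5 analyses visits as nominal and lets Visit 6 fall earlier for those who discontinue; SAP 2.2.6 and 2.2.10 speak of Week 8/Exit.
- Suggesting no: SAP 2.2.12.1 defines the outcome at Week 8 and says the model estimates the Week 8 effect; 2.2.6 has GENMOD account for early withdrawal; 2.2.12.2 lists the last treatment visit apart from Week 8. That last item is weaker evidence, since it could also serve patients with no exit visit.
- No sentence decides between them.

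**3. Scale, from the protocol's own inputs (12.3)**

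Rates 21.6% and 11.8%, 100 per arm, two-sided 5%. Power by the pooled-variance test is 45.9%, which reproduces the stated 45%. The standard error of the difference is √(0.216×0.784/100 + 0.118×0.882/100) = √0.002734 = 0.052, or 5.2 points, against a difference of 21.6 − 11.8 = 9.8 points.

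**4. Illustrative simulation**

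Neither document gives a dropout rate, so everything here is assumed. There are two arms. Latent severity at Weeks 2, 4, 6 and 8 has autocorrelation 0.7, and response rises linearly to 21.6% and 11.8%. Dropout occurs after Weeks 2, 4 or 6, and the exit score equals the last visit's score. The GEE has unstructured correlation, no baseline covariate and no patient replacement. Large-sample results use 600,000 per arm.

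- Dropout following prior IGA response: GEE bias 0.2 point or less in every pattern tried.
- Dropout following severity (logit slope 1 per SD):

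| Dropout, active/placebo | GEE bias (points) | Shift if exit scores count as Week 8 (points) |
|---|---|---|
| 10%/10% | +0.3 | −0.8 |
| 20%/20% | +0.5 | −1.7 |
| 30%/30% | +0.8 | −2.6 |
| 20%/10% | +1.1 | −2.8 |
| 10%/20% | −0.2 | +0.3 |
| 31%/7% | +2.1 | −5.4 |
| 7%/31% | −1.0 | +2.1 |

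In 2,000 simulated trials of 100 per arm, the two readings of the exit score disagreed at p<0.05 in 4–7% of trials with equal dropout of 10–20%, and in 11–12% at 10% v 20%.

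**5. Jump-to-reference at 20% dropout**

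If those who drop out are average patients, the active rate becomes 0.8×21.6 + 0.2×11.8 = 19.64%, a difference of 19.64 − 11.8 = 7.8 points. In the simulation, where sicker patients leave, it is 8.7 points. Both are below the full-adherence 9.8.

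**6. What the extreme-case analysis shows**

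Take 10 missing per arm, so 90 observed: 0.216×90 ≈ 19 and 0.118×90 ≈ 11 responders. Scenario 1 (active worst, placebo best) is 19 v 21 of 100, p = 0.86. Scenario 2 is 29 v 11, p = 0.002. Relaxed, Scenario 2 stays significant at 23 v 11 (p = 0.037) and fails at 22 v 11 (p = 0.056). These bounds are useful as a tipping analysis, but they do not estimate the de facto effect.

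**The case against.** **The GEE does little harm.** This stands in large part. Bias is 0.2 point or less when dropout follows prior response, and 0.8 or less when it follows severity with equal dropout up to 30%. A reader might infer from the MCAR statement that the primary analysis is badly biased or rejects too often; neither the documents nor these calculations support that.

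**The SAP does address MNAR.** It does, and it would be wrong to say otherwise. The relaxation step is informative and worth keeping. It answers a different question from jump-to-reference.

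**The primary endpoint is plainly at Week 8.** SAP 2.2.12.1 is the strongest text for excluding exit scores. It is therefore too strong to say that earlier scores will enter the primary endpoint. They could, because the nominal-visit rule in 2.2.5 is not qualified.

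**The interim triggers agree.** A reader might see a contradiction between Protocol 12.5 (completed Week 8 assessments) and SAP 2.2.10 (Week 8/Exit). That is not established. Protocol 7.5 gives early leavers the Week 8 assessments, and Protocol 8.2.7 and the flow chart combine Week 8 with early termination. The trigger is ambiguous in the same way as the endpoint. If exits count, and everyone who leaves attends one, 150 patients at 20% dropout would hold 150×0.8 = 120 true Week 8 scores.

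**The simulation is not the trial.** Correct. The SAP model adjusts for baseline IGA and severity, there are three arms, and Protocol 6.1 and 7.6 provide for replacing some patients. The figures indicate scale only. The 5.4-point shift needs 31% v 7% dropout, for which the documents give no basis.

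**Jump-to-reference already names its group.** Protocol 12.9.2 does tie it to patients who discontinue drug. What remains open is the use of scores observed after stopping.

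**Conclusion.** The point holds as a conflict between documents and a gap in a definition. The SAP as written omits the protocol's de facto analysis and rests the primary analysis on a stronger assumption than the protocol's, with no reason in the text available. The SAP's front matter is not part of that text, so it cannot be said that no reason exists anywhere.

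Of the two numerical issues, the exit-score rule matters more than MCAR against MAR. With equal dropout of 10–30% it lowers the estimate by 0.8 to 2.6 points, which is at most half of the 5.2-point standard error; the shift is larger only under some patterns of unequal dropout. These sizes rest wholly on the assumed dropout and severity model. The plan should be corrected, but it is not invalid, and no inflation of false positives is claimed.

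**What to change.** Before any unblinding, including for the interim analysis:

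1. **SAP 2.2.6.** Reinstate jump-to-reference on the FAS. Because the endpoint is yes/no, apply it to the IGA score and then derive response. Keep the extreme-case/relaxation analysis as the tipping analysis.
2. **SAP 2.2.5.** State that an early-termination score taken before the Week 8 window is not the Week 8 value, is kept at its actual time, and feeds only the last-treatment-visit endpoint. Use one definition for the interim count in SAP 2.2.10 and Protocol 12.5.
3. **Primary analysis.** Align SAP 2.2.12.1 with the protocol's MAR analysis, or amend Protocol 12.9.2 with a reason. Copying the protocol model back is not enough: it names treatment-by-visit as the random effect and mentions no patient effect, so it needs full specification. No particular imputation method is required.
4. **Scores after stopping drug.** For each estimand, say how an observed Week 8 score is used. Label any as-observed use as treatment policy, separate from the full-adherence and jump-to-reference estimands.

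The cost is SAP wording, one protocol alignment and modest programming, with no new data or patients. The de facto estimate will be somewhat smaller: about 7.8 to 8.7 points against 9.8 at 20% dropout, depending on who leaves.
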